Death, MI, and stroke will be evaluated at 3 years from the last patient randomized, where subjects contribute data from time of enrollment until the occurrence of MACCE or three year follow-up, whichever occurs first. Subjects who die or are lost to follow up before this time will be censored at their last recorded activity. This secondary endpoint is not a co-primary endpoint because we would need to adjust for multiplicity and this would increase our sample size.

Other Secondary Endpoints

- Comparison of proportion of patients in each arm with MACCE at one year, excluding patients lost to follow-up from each arm
- MACCE rate at each time point besides one year
- Rate of each individual component of MACCE at each time point
- Rate of death, MI, and stroke at each time point
- Rate of death and MI at each time point
- Rate of cardiac death alone and in combination with other end points
- Rate of death, MI, stroke and all repeat revascularizations at each time point
- Stent thrombosis (ARC definition) and graft occlusion at each time point
- Bleeding complication
- Significant arrhythmia
- Development of acute renal failure
- Length of hospital stay
- Rehospitalization within 30 days and 1 year of the primary procedure

- Usefulness of the STS, logistic Euroscore, SYNTAX score, clinical SYNTAX score, ACEF score, Functional SYNTAX score and other scoring systems for predicting outcomes
- Outcomes based on left internal mammary artery use alone versus multiple arterial conduits
- Cost and cost-effectiveness at each time point
- Health-related quality of life index (EQ-5D) at each time point
- Functional class at each time point
- Number of anti-anginal medications at each time point.

Pre-specified Subgroup Analyses

These analyses will be performed between the PCI and CABG arms, as well as within each arm, as appropriate.

- Comparison of outcomes by baseline features including diabetes status, sex, age, ejection fraction, kidney function, acute coronary syndrome, prior MI, and geographic location (within or outside of the United States).
- Comparison of outcomes by STS, logistic Euroscore, SYNTAX score, clinical SYNTAX score, ACEF score and Functional SYNTAX score
- Comparison of outcomes by revascularization status (i.e., complete or incomplete as defined by angiogram)
- Compare complete arterial revascularization to incomplete arterial revascularization in the CABG group
- Compare on-pump to off-pump CABG results
- Comparison of outcomes by proximal LAD versus non proximal LAD
- Comparison of surgical results between patients with FFR measured before CABG and angiography-guided CABG

10. Statistics

Null and Alternative Hypotheses to Address Primary Question

The study makes use of a noninferiority design and assumes that a hazard ratio of 1.65 or less is not clinically meaningful. More specifically, the null hypothesis is that the hazard of MACCE for PCI patients is greater than that of CABG patients and the alternative hypothesis is that the hazard of MACCE for PCI is not worse (not greater) than that for CABG patients. Let HR_0 be the non-inferiority margin – i.e., the maximum ratio of clinical insignificance. Then the null (H0) and alternative (H1) hypotheses can be expressed as:

$$H_0: HR \geq HR_0 \text{ vs } H_1: HR < HR_0$$

Primary Analysis Plan: Statistical Tools and Test Statistic

The primary analysis will be based on the intention-to-treat (ITT) principle, whereby all randomized patients will be included in the analysis and according to the treatment group to which they were originally allocated. Patients will be encouraged to remain in the trial until completion of up to 5 years follow-up. All patients will be followed for 5 years post-randomization or until they die, whichever comes first. If a patient refuses further clinical follow-up, the follow-up evaluation will be conducted using telephone interviews. For patients who drop out or are lost to follow-up, the reason for dropping out or being lost will be recorded. Importantly, for the primary analysis the patient will be censored at the time when the last follow-up examination or telephone contact took place if the subject did not experience MACCE, allowing the subject to be included in the analysis according to the ITT analysis plan.

Kaplan-Meier curves will be used to graphically display differences in MACCE by treatment arm and by diabetes status. In addition, we will use survival analytic techniques such as a log-rank test or, if appropriate, a Cox proportional hazards (PH) model to estimate the difference in hazard of MACCE by treatment arm, stratified by center, and with diabetes status included as a term in the model. The test for non-inferiority of fractional flow reserve-guided PCI will be one-sided and assessed at the 0.025 level of significance. For example, a Cox PH model for the hazard of MACCE can be expressed as:

$$\lambda_1 = \lambda_{0i} \exp(\beta_1 PCI + \beta_2 DM)$$

for $i=1, 2, \dots, 50$ where i indexes the clinical sites involved in the study, PCI represents an indicator for whether a subject has been randomized to the PCI arm, DM is an indicator for whether the subject has been diagnosed with diabetes at baseline, λ_1 , represents the hazard of MACCE, and λ_{0i} represents the baseline hazard of MACCE at the i^{th} clinical site. Our model allows the baseline hazard of MACCE to vary by clinical site. Our interest lies in inference about β_1 , which represents the difference in log-hazard between the treatment arms. A Wald test statistic that is a function of β_1 can then be used to assess whether the hazard ratio for the treatment arms is within the non-inferiority margin. For this purpose, we will conduct a one-sided test at the 0.025 level of significance.

Model Diagnostics: Assessing heterogeneity of hazards across levels of confounders and assessing adherence to the proportional hazards assumption

We will perform a number of tests to confirm that the assumptions in the above model are reasonable. If the number of subjects per site is too small, we will pool smaller sites so that there are at least 10 subjects per site. Then, to confirm that the hazard of MACCE does not vary by pooled site, diabetes status and gender, we will include an interaction term between pooled site, PCI and diabetes and test whether the corresponding coefficient is greater than zero using a two-sided Wald test statistic at the 0.15 level of significance. We will take a similar approach by including an interaction term between gender and PCI. If homogeneity of the hazard by a feature is rejected, the corresponding interaction term will be included in the model. The test statistic corresponding to the primary question of interest (i.e., the treatment effect) will be evaluated in the presence of the interaction term to describe the overall treatment effect. We will additionally present the hazard ratios by levels of the modifying factor.

The proportional hazards assumption will be evaluated through graphical techniques including plots of transformed survival estimates (i.e., $\log(-\log(\text{survival at time } t))$) by log-transformed time and Kaplan-Meier curves by treatment arm. Should the assumption be violated, we can relax the assumption through inclusion of an interaction term between treatment arm and log-transformed time.

Sample Size and Power Considerations¹⁷

Recently, the EXCEL¹⁸, NOBLE¹⁹ and BEST²⁰ trials have been published. These studies demonstrate a one year MACCE rate which is in the 10% or lower range in the CABG arm, compared with the SYNTAX and FREEDOM trials which were in the 12% range. In addition, in EXCEL, a clinically acceptable non-inferiority margin for death, CVA and MI was a hazard ratio in the 1.4 range. Because of the lower event rates after CABG in more recent studies and because we will also be including revascularization as part of MACCE, the Steering Committee feels a hazard ratio of 1.65 is more appropriate for defining a clinically acceptable non-inferiority margin. We assume a 10% of subjects in the CABG arm experience MACCE, and further that patients in the PCI arm will not experience a higher rate than those in the CABG arm. We would deem an increase in event rate up to and including a 16% event rate as not clinically inferior. Thus, given a clinically irrelevant hazard ratio of 1.65, a one-sided 2.5% significance level and 90% power to reject the null hypothesis if it is false, the sample size necessary is 645 patients per group (1290 for the entire study). These calculations are based on assumptions of uniform accrual over time, no loss to follow-up, exponentially distributed death times, and a Wald test statistic. Thus, to account for patients lost to follow-up and subject withdrawal we will enroll up to 1500 patients from up to 50 medical centers.

Sensitivity Analyses

Our current approach is to do an intent-to-treat analysis and include all randomized subjects in the analysis. Subjects who are lost to follow-up will be included in the analysis up to the time they are censored. An alternative set of analyses that will serve as sensitivity analyses will be to compare the proportion of subjects who experience the primary event at one year of follow-up by treatment arm using logistic regression techniques, where subjects who are lost to follow-up are excluded from the analysis, or included with an imputed outcome using multiple imputation techniques that rely on missing at random and missing not at random techniques. Auxiliary variables to be used in the multiple imputation include all baseline variables such as age, gender, site, diabetes status, etc. This will allow comparisons to our primary analysis. If results are similar across analyses, this will bolster our findings. If they are different, we will report the discrepancy. The results from our primary analysis, however, will be reported as our final analysis.

Secondary Analyses

Secondary analyses will be performed to inform future studies and are therefore considered hypothesis-generating. For example, we will use Cox proportional hazards regression techniques to assess whether the differences in hazard of the key secondary outcome of death, MI, and stroke (censored at 3 years) is different by treatment arms. Similarly, we will use these tools to investigate whether relationships between outcome and treatment vary by baseline features such as age, sex, geographic location, etc.

11. Appendix A.

Definitions

Death is defined as all cause death. Cardiac death is defined as any sudden death, death related to acute myocardial infarction, arrhythmia or congestive heart failure, death secondary to a cerebrovascular accident, or death directly related to PCI or CABG, even if the ultimate cause of death is not clearly a cardiac event (e.g., infection). Non-cardiac death is any death which is not clearly cardiac in etiology.

Myocardial infarction is defined in two ways, depending on whether or not it is PCI or CABG-related or a spontaneous event, as recently described in the literature.²¹

Spontaneous myocardial infarction (>72 hours after PCI or CABG):

Detection of rise and/or fall of cardiac biomarkers (CK-MB or troponin) with at least one value above the 99th percentile of the upper reference limit (URL) together with evidence of myocardial ischemia with at least one of the following:

- Symptoms of ischemia
- ECG changes indicative of new ischemia [new ST-T changes or new, persistent, non rate-related left bundle branch block (LBBB)]
- Development of pathological Q waves (≥ 0.03 seconds in duration and ≥ 1 mm in depth) in ≥ 2 contiguous precordial leads or ≥ 2 adjacent limb leads of the ECG
- Imaging evidence of new loss of viable myocardium or new regional wall motion abnormality

PCI or CABG-related MI (<72 hours after PCI or CABG):

Elevation of the cardiac troponin value $> 10 \times 99^{\text{th}}$ percentile of the URL in patients with a normal baseline reference level, or an increase of $> 20\%$, if the baseline values are elevated, but are stable or falling. In addition, at least one of the following:

- (i) new pathologic Q waves or new left bundle branch block
- (ii) angiographic documented new graft or new major native coronary occlusion
- (iii) imaging demonstration of new loss of viable myocardium or new regional wall motion abnormalities is required.

Stroke (cerebrovascular accident or CVA) is the rapid onset of a focal or global neurological deficit. If the duration is <24 hours, the event is deemed a transient ischemic attack (TIA), except if an intervention is performed as defined below. If the duration is ≥ 24 hours, it is deemed a stroke. Stroke is subdivided as ischemic, hemorrhagic, or undetermined. Ischemic stroke refers to acute symptomatic episode of focal cerebral, spinal, or retinal dysfunction caused by an infarction of the central nervous system tissue. Hemorrhagic stroke is an acute symptomatic episode of focal or global cerebral or spinal dysfunction caused by nontraumatic intraparenchymal, intraventricular or subarachnoid hemorrhage. Undetermined stroke is one with insufficient information to allow categorization as either of the above two.

Stroke is diagnosed when the following criteria are met:

1. Rapid onset of a focal/global neurological deficit with at least one of the following:
 - Change in level of consciousness
 - Hemiplegia
 - Hemiparesis
 - Numbness or sensory loss affecting one side of the body
 - Dysphagia/aphasia
 - Hemianopia
 - Amaurosis fugax
 - Other new neurological sing(s)/symptom(s) consistent with stroke

2. Duration of focal/global neurological deficit is ≥ 24 hours, or it can be < 24 hours if a therapeutic intervention is performed, brain imaging clearly documents a new hemorrhage or infarct, or the neurological deficit results in death.
3. Confirmation of the diagnosis by at least one of the following:
 - Neurology or neurosurgical specialist
 - Brain imaging (CT, MRI, or cerebral vessel angiography)
 - Lumbar puncture diagnostic of intracranial hemorrhage

Urgent revascularization is defined as an unplanned hospitalization for an acute coronary syndrome with at least one of the following: electrocardiographic changes, biomarker elevation, or new perfusion/wall motion abnormalities to document ischemia and which results in revascularization during the hospitalization.

Repeat revascularization is defined as any unplanned (elective or urgent) revascularization, whether PCI or CABG. Planned staged PCI procedures do not qualify.

Bleeding is defined as per the Bleeding Academic Research Consortium (BARC).²² Other descriptions of bleeding, such as TIMI, will be applied as well.

BARC Bleeding Definitions:

Type 0: no bleeding

Type 1: bleeding that is not actionable and does not cause the patient to seek unscheduled performance of studies, hospitalization, or treatment by a healthcare professional; may include episodes leading to self-discontinuation of medical therapy by the patient without consulting a healthcare professional

Type 2: any overt, actionable sign of hemorrhage (eg, more bleeding than would be expected for a clinical circumstance, including bleeding found by imaging alone) that does not fit the criteria for type 3, 4, or 5 but does meet at least one of the following criteria: (1) requiring nonsurgical, medical intervention by a healthcare professional, (2) leading to hospitalization or increased level of care, or (3) prompting evaluation

Type 3

Type 3a

Overt bleeding plus hemoglobin drop of 3 to < 5 g/dL* (provided hemoglobin drop is related to bleed)

Any transfusion with overt bleeding

Type 3b

Overt bleeding plus hemoglobin drop ≥ 5 g/dL* (provided hemoglobin drop is related to bleed)

Cardiac tamponade

Bleeding requiring surgical intervention for control (excluding dental/nasal/skin/hemorrhoid)

Bleeding requiring intravenous vasoactive agents

Type 3c

Intracranial hemorrhage (does not include microbleeds or hemorrhagic transformation, does include intraspinal)

Subcategories confirmed by autopsy or imaging or lumbar puncture

Intraocular bleed compromising vision

Type 4: CABG-related bleeding

Perioperative intracranial bleeding within 48 h

Reoperation after closure of sternotomy for the purpose of controlling bleeding

Transfusion of ≥ 5 U whole blood or packed red blood cells within a 48-h period†

Chest tube output ≥ 2 L within a 24-h period

Type 5: fatal bleeding

Type 5a

Probable fatal bleeding; no autopsy or imaging confirmation but clinically suspicious

Type 5b

Definite fatal bleeding; overt bleeding or autopsy or imaging confirmation

Stent thrombosis is defined as per the Academic Research Consortium.²³

ARC Definitions:

Definite stent thrombosis

1. Angiographic confirmation of stent thrombosis
2. The presence of a thrombus that originates in the stent or in the segment 5 mm proximal or distal to the stent and presence of at least 1 of the following criteria within a 48-hour time window:
 - Acute onset of ischemic symptoms at rest
 - New ischemic ECG changes that suggest acute ischemia
 - Typical rise and fall in cardiac biomarkers (refer to definition of spontaneous MI)
 - Nonocclusive thrombus
 - Intracoronary thrombus is defined as a (spheric, ovoid, or irregular) noncalcified filling defect or lucency surrounded by contrast material (on 3 sides or within a coronary

stenosis) seen in multiple projections, or persistence of contrast material within the lumen, or a visible embolization of intraluminal material downstream.

- Occlusive thrombus
- TIMI 0 or TIMI 1 intrastent or proximal to a stent up to the most adjacent proximal side branch or main branch (if originates from the side branch).
- Pathological confirmation of stent thrombosis
- Evidence of recent thrombus within the stent determined at autopsy or via examination of tissue retrieved following thrombectomy.

Probable stent thrombosis

Clinical definition of probable stent thrombosis is considered to have occurred after intracoronary stenting in the following cases:

- Any unexplained death within the first 30 days
- Irrespective of the time after the index procedure, any MI that is related to documented acute ischemia in the territory of the implanted stent without angiographic confirmation of stent thrombosis and in the absence of any other obvious cause

Possible stent thrombosis

Clinical definition of possible stent thrombosis is considered to have occurred with any unexplained death from 30 days after intracoronary stenting until end of trial follow-up.

Graft Occlusion is defined based on an ARC-like definition²⁴

Definite graft occlusion

1. Clinical presentation of acute coronary syndrome with graft occlusion confirmed by angiography, multi-slice CT or autopsy
2. Q-wave MI in the territory of one or more of the treated vessels within the first 30 days

Probably graft occlusion

1. Any unexplained death within 30 days of CABG
2. Any MI that is related to documented acute ischemia in the territory of the anastomosed graft without angiographic confirmation of graft occlusion

Possible graft occlusion

1. Any unexplained death beyond 30 days

Significant Arrhythmia consists of ventricular tachycardia or fibrillation requiring cardioversion, atrial fibrillation lasting > 24 hours, or need for a permanent pacemaker.

Acute Kidney Injury AKI (acute kidney injury) is defined as any of the following:

- K Increase in SCr (Serum creatinine) by ≥ 0.3 mg/dl (≥ 26.5 $\mu\text{mol/l}$) within 48 hours;
- or K Increase in SCr to ≥ 1.5 times baseline, which is known or presumed to have occurred within the prior 7 days;
- or K Urine volume < 0.5 ml/kg/h for 6 hours.

Rehospitalization is defined as a hospital stay of > 36 hours.

Cross-over

If, during the first month after randomization, a patient receives as the initial revascularization therapy the alternative form of revascularization than the assigned treatment (i.e. Randomized to CABG but receives PCI), this will be defined as a cross-over and not a repeat revascularization event, unless the reason for the alternative revascularization strategy is due to a change in the patient's clinical status resulting in urgent/emergent revascularization.

12. References

¹ Fihn SD, Gardin JM, Abrams J, Berra K, Blankenship JC, Dallas AP, Douglas PS, Foody JM, Gerber TC, Hinderliter AL, King SB 3rd, Kligfield PD, Krumholz HM, Kwong RY, Lim MJ, Linderbaum JA, Mack MJ, Munger MA, Prager RL, Sabik JF, Shaw LJ, Sikkema JD, Smith CR Jr, Smith SC Jr, Spertus JA, Williams SV, Anderson JL. 2012 ACCF/AHA/ACP/AATS/PCNA/SCAI/STS guideline for the diagnosis and management of patients with stable ischemic heart disease: a report of the American College of Cardiology Foundation/American Heart Association task force on practice guidelines, and the American College of Physicians, American Association for Thoracic Surgery, Preventive Cardiovascular Nurses Association, Society for Cardiovascular Angiography and Interventions, and Society of Thoracic Surgeons. *Circulation* 2012;126:e354-471.

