Design	
The FAME 3 trial is a multicenter, international, randomized, controlled noninferiority trial. All patients with multivessel CAD (not involving the left main) will be screened by the site's Heart Team (including but not limited to an interventional cardiologist, cardiac surgeon and research coordinator). If all agree that the patient can be treated either with FFR-guided PCI or CABG, and all inclusion criteria are met and no exclusion criteria are met, then the patient will be randomized.
 
Baseline clinical, functional, laboratory and electrocardiographic data will be obtained. Patients will receive treatment within 4 weeks of randomization. Patients randomized to CABG will receive state of the art therapy at the discretion of the local surgeon with a strong emphasis on arterial revascularization. Patients undergoing PCI will have FFR measured with a Abbott coronary pressure wire across all lesions. If the FFR is ≤ 0.80, then PCI will be performed with the Medtronic Resolute Integrity/Onyx drug-eluting stent (DES) as per usual routine. If the FFR is > 0.80 then PCI will be deferred.
 
Post procedure laboratory tests will be obtained including troponin within 12-24 hours after the procedure. Resource utilization will be obtained. All patients will receive medical therapy as per published guidelines.
 
Patients will follow-up at 1 and 6 months, and 1, 2, 3, and 5 years with an evaluation of clinical status, functional status, medications and events.
 
Core lab analyses will include formal quantitative coronary angiography (QCA) of the baseline angiograms with calculation of the Synergy between Percutaneous Coronary Intervention with Taxus and Cardiac Surgery (SYNTAX) score and Functional SYNTAX Score.

Population	A complete listing of all inclusion and exclusion criteria can be found in section 5 of the protocol.
Duration	Ten years: 5 years of enrollment and 5 years follow-up from last patient enrolled.
Primary Endpoint	Death, MI, stroke and any repeat revascularization (MACCE) will be evaluated at 1 year, where subjects contribute data from time of randomization until the occurrence of MACCE or one year follow-up,

	whichever occurs first. Subjects who die or are lost to follow up before 1 year will be censored at their last recorded activity.

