The Fractional Flow Reserve versus Angiography for Multivessel Evaluation (FAME) trial, randomized 1005 patients with two or three vessel coronary disease and stable symptoms or non ST elevation acute coronary syndromes in whom PCI was indicated to either angiography-guided PCI or to FFR-guided PCI, in which case FFR was measured across every lesion and PCI was performed only if the FFR was ≤ 0.80 .¹² The one year primary endpoint of death, MI or the need for repeat revascularization occurred in significantly fewer patients randomized to the FFR-guided strategy (13.2 vs. 18.3%, $p=0.02$). This was driven by numerical reductions in all three components of the primary endpoint: death (1.8 vs. 3.0, $p=0.19$), MI (5.7 vs. 8.7%, $p=0.07$) and repeat revascularization (6.5 vs. 9.5, $p=0.08$). The composite of death and MI was significantly reduced by FFR-guided PCI (7.3 vs. 11.1, $p=0.04$).

Figure 1 One year outcomes from FAME 1 Trial

[figure not shown]

At two year follow-up, there continued to be a significant reduction in death and MI with FFR-guided PCI (8.4 vs. 12.9%, $p=0.02$) and a trend towards a lower rate of death, MI or the need for repeat revascularization (17.9 vs. 22.4%, $p=0.08$).¹³ The improved outcomes with FFR-guided PCI are likely a result of more judicious PCI whereby ischemia-producing lesions are

revascularized and non-ischemia producing ones are treated medically. In this manner, the benefit of PCI can be maximized by relieving ischemia and the risks can be minimized by avoiding unnecessary PCI.

This difference between functional complete revascularization with FFR-guided PCI and anatomic complete revascularization with angiography guidance was further demonstrated by a substudy from FAME evaluating the so-called Functional SYNTAX Score (FSS).¹⁴ In this substudy, the SYNTAX score was calculated in the usual fashion in the 497 patients in FAME who were randomized to FFR guidance. The FSS was then calculated in these patients by subtracting the points for any lesions incorporated into the SYNTAX score in which the FFR was >0.80 . The FSS resulted in reclassification of 32% of patients from a higher risk SYNTAX score tertile to a lower risk FSS tertile. The FSS was a better discriminator of the risk for death and MI or death, MI and the need for repeat revascularization as compared to the SYNTAX score.

Figure 2 Comparison of Functional SYNTAX Score and SYNTAX Score in FAME 1 Trial

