- Laboratory studies including complete blood count, basic metabolic panel, lipid panel and glycosylated hemoglobin (HgbA1C); all hospitalized patients will have cardiac markers, including troponin checked, and if elevated, repeated 4-12 hours later to determine if they are stable or declining
- Electrocardiogram
- Quality of life (EQ-5D) assessment

Coronary Artery Bypass Graft Surgery (CABG)

CABG will be performed as per clinical routine at each participating center. FFR assessment of lesions to help guide bypass is not mandated, but if performed at the time of the diagnostic angiogram, the information can be used by the surgeon. We expect this will occur in approximately ¼ of cases, and in most of these cases we expect the decision to place a bypass graft will be based on the FFR result. Adjunctive pharmacologic therapy during and immediately after the CABG should be prescribed as per the clinical routine at each participating center. Recommendations are described in the section Medications.

Both off-pump and on-pump surgery are acceptable, as long as the surgeon and the site are experienced in the particular technique. An internal mammary graft to the LAD should be attempted in all cases, if feasible. Complete arterial revascularization is strongly recommended,

however, each center should use a conduit strategy with which they are most comfortable. All vessels ≥ 1.5 mm in diameter and with $\geq 50\%$ stenosis should undergo bypass procedure, if technically feasible.

Fractional Flow Reserve-Guided PCI

Access:

- PCI can be performed via the radial artery or the femoral artery, as per the site's usual routine.

Performance of FFR:

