- If the FFR in a vessel is ≤ 0.80 , the operator is not obligated to stent. For example, if on pullback of the wire, diffuse disease is diagnosed without an obvious focal step-up, stenting is not mandated. Or if a small sidebranch of a bifurcation lesion has an FFR ≤ 0.80 , stenting is not mandated. In other words, operators should use their good clinical judgment and follow their routine practice.
- In case of serial stenoses, FFR “of the complete vessel” should be ≤ 0.80 to warrant PCI of one of more of these stenoses. Long stents to cover a segment or multiple shorter stents, can be placed at the discretion of the operator. After treating one stenosis, FFR should be remeasured to determine whether the second stenosis warrants therapy.
- In the case in which the operator decides to revascularize a chronic total occlusion, FFR measurement is not mandatory and a default FFR value of 0.50 can be applied.
- It is strongly advocated to measure the final post DES implantation FFR, to document the degree of resolution of the pressure gradient achieved by the revascularization. A pullback should be performed to address the source of any residual gradient and to check for drift in the pressure wire.
- Based on the literature and clinical experience, we expect a $<1\%$ complication rate from FFR measurement.¹⁵

PCI Strategy:

- PCI will be performed solely with the Medtronic Resolute Integrity/Onyx stent. If the Resolute stent cannot be delivered, an alternative current generation drug-eluting stent can be substituted, preferably an everolimus eluting stent.
- Covering the entire diseased portion of the lesion with a single drug-eluting stent is recommended.
- A single cross-over stent strategy for bifurcation lesions is recommended, with provisional sidebranch stenting only if < TIMI 2 flow is persistent after kissing balloon inflation of the sidebranch.
- It is not recommended to revascularize a chronic total occlusion (CTO) unless a patient has persistent symptoms after the initial PCI, documented ischemia on noninvasive testing involving the region subtended by the vessel with the CTO, and visible collaterals which fill a vessel >2.5 mm in diameter. If the operator is considering bringing the patient back for revascularization of a CTO, this should be documented in the CRF at the time of the baseline procedure. The operator is not obligated to bring the patient back, but this will avoid confusion regarding whether or not the follow-up procedure is planned.

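### The subgroup list allows PCI-versus-CABG comparison within strata of angiographic completeness, which randomization does not protect, and by a Functional SYNTAX score that most CABG patients will lack

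*Combined protocol and SAP*

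**What the plan says.** One sentence in section 9, Pre-specified Subgroup Analyses, governs the whole list: "These analyses will be performed between the PCI and CABG arms, as well as within each arm, as appropriate". Two entries matter here: "Comparison of outcomes by revascularization status (i.e., complete or incomplete as defined by angiogram" and "Comparison of outcomes by STS, logistic Euroscore, SYNTAX score, clinical SYNTAX score, ACEF score and Functional SYNTAX score". Neither names an arm. Three other procedural entries (completeness of arterial grafting, pump use, FFR before surgery) are worded as comparisons among CABG patients. Appendix A does not define complete revascularization.

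The treatment rules are in the Protocol Summary and section 6:

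- **CABG:** vessels of at least 1.5 mm with 50% or more "stenosis should undergo bypass procedure, if technically feasible".
- **PCI:** where FFR exceeds 0.80, "then PCI will be deferred". The operator may also leave a vessel unstented at 0.80 or below, for example in diffuse disease. On occlusions: "It is not recommended to revascularize a chronic total occlusion (CTO) unless" a set of listed conditions is met.

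FFR is planned across all lesions in the PCI arm, with failure expected in 5% of lesions. In the CABG arm it is optional and may be used if done at the diagnostic angiogram: "We expect this will occur in approximately ¼ of cases". Section 3 defines the Functional SYNTAX score as the SYNTAX score less the points for lesions with FFR above 0.80. It reports from an earlier trial: "The FSS resulted in reclassification of 32% of patients from a higher risk SYNTAX score tertile to a lower risk FSS tertile". The plan has no scoring rule for a patient without FFR.

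Section 10, Secondary Analyses, calls these analyses hypothesis-generating and speaks of treatment effects varying by baseline features.

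**The concern.** A treatment comparison inside a subgroup keeps the protection of randomization only if membership does not depend on the assigned arm. Completeness judged by angiogram does depend on it. The same patient, with one angiographically significant lesion whose FFR is above 0.80, would tend to be complete after CABG and incomplete after protocol-compliant PCI. Section 3 itself contrasts functional with anatomic completeness, yet the subgroup uses only the anatomic standard.

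The Functional SYNTAX score raises a different question. It is not a result of treatment, but the measurement behind it is planned for one arm and optional in the other.

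What is at stake is interpretation. Because the analysis is pre-specified, an apparent advantage or harm of PCI in incompletely revascularized or high-score patients could be read as evidence on whom to treat by which method. A larger sample would not remove the bias.

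**Working it through.** The plan gives no figure for these subgroups, so the first step is to compare the variables.

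| Variable | When fixed | CABG arm | PCI arm |
|---|---|---|---|
| Core-lab angiographic SYNTAX score | Baseline angiogram | All patients | All patients |
| Functional SYNTAX score | When lesion FFR is measured, before stenting | About 1/4 of patients | Planned for all lesions; 5% of lesions fail |
| Angiographic completeness | After the procedure, up to 4 weeks after randomization | Anatomic rule | FFR rule plus occlusion rule |

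Only the first row is a baseline variable measured alike in both arms. Completeness also has a timing gap: follow-up starts at randomization, so a patient who dies before the procedure has no category.

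**Completeness: can a spurious effect arise?** This is an illustration; every input except the 10% event rate is an assumption. Give each patient a standard-normal complexity U and a one-year risk of 1 − exp(−exp(a + b·U)), with a set so that mean risk is 10%. Treatment has no effect on anyone. Let the probability of completeness be logistic in U, with slope −1 (linked) or 0 (not linked) in each arm. The apparent HR is log(1 − p_PCI)/log(1 − p_CABG) within each stratum. Selected results from 2,000,000 draws:

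| Risk HR per SD, exp(b) | CABG complete | PCI complete | Linked to U in | HR, complete | HR, incomplete |
|---|---|---|---|---|---|
| 1.5 | 80% | 80% | both | 1.000 | 1.000 |
| 1.5 | 80% | 50% | both | 0.904 | 0.893 |
| 2.0 | 90% | 20% | both | 0.655 | 0.652 |
| 2.0 | 80% | 80% | CABG only | 1.151 | 0.648 |
| 2.0 | 80% | 80% | PCI only | 0.869 | 1.543 |
| 2.0 | 90% | 20% | CABG only | 1.079 | 0.593 |
| 2.0 | 90% | 20% | PCI only | 0.607 | 1.101 |

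Over the whole grid (CABG complete 80-90%, PCI 20-80%, risk HR 1.5-2.0) the range is 0.61 to 1.15 among complete and 0.59 to 1.54 among incomplete patients. In rows 2 and 3 PCI looks better in both strata although it has no effect: the PCI complete group is more selected, and the PCI incomplete group has taken in lower-risk patients. The bias is absent when completeness depends on risk identically in both arms (row 1). It would also be absent if completeness were unrelated to risk in both.

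**Functional SYNTAX score: precision.**

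- Formula check against the plan's sample size: events = 4 × (1.960 + 1.282)² / (ln 1.65)² = 167.6. Dividing by the mean of 10% and 16% gives 167.6/0.13 = 1289, or 645 per group, as stated in section 10.
- CABG patients with FFR: 750 × 1/4 = 187.5, about 188. Events at 10%: 18.75, about 19.
- With all 750 PCI patients scored and 10% in both arms, events = 937.5 × 0.10 = 93.75, of which the CABG share is 187.5/937.5 = 0.20.
- z = ln 1.65 × √(93.75 × 0.20 × 0.80) − 1.960 = 0.5008 × 3.873 − 1.960 = −0.02, so power against the 1.65 margin is about 49% before any split by score.
- At the Summary's 12% rate there are 112.5 events, z = 0.5008 × √18 − 1.960 = 0.16, and power is about 57%.

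**Functional SYNTAX score: bias.** Same null model, true HR 1.00, risk HR 1.5-2.0 per SD of score, upper third called high:

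- Measured CABG quarter is a random sample, others excluded: HR 1.00. No bias.
- Measurement depends on another risk factor (assumed HR 1.5 per SD; log-odds of measurement ±0.5 to ±1 per SD): HR about 0.79 to 1.30.
- Unmeasured CABG patients keep their angiographic score (modelled as 32% of those truly in lower strata placed high): HR about 1.19 to 1.29 in the high stratum and 1.00 below it.

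**The case against.** The governing sentence ends with a qualifier, and it must do some work, since the list contains items that exist only in the CABG arm. The revascularization entry can be read as complete versus incomplete within an arm. Section 10 names only baseline features when it describes variation in treatment effect, and it labels secondary analyses as hypothesis-generating. The primary intention-to-treat comparison does not involve these variables. All of this stands, and it limits the consequence. It does not settle the reading: the CABG-only items say so, this one does not, and nothing states which entries are appropriate between arms.

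A reader might infer more than the documents support:

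- **That the Functional SYNTAX comparison is biased by construction.** It is not. The score comes from FFR taken before treatment. In CABG patients that is FFR from the diagnostic angiogram, which the protocol places before Heart Team review and enrolment, so assignment cannot drive who was measured. No passage says the measured quarter is unrepresentative.
- **That 32% of PCI but only 8% of CABG patients (0.25 × 0.32) move to a lower stratum.** The fourfold ratio is simply 1/0.25, and the 32% cancels. The 8% needs a scoring rule that the plan does not contain, and the 32% comes from an earlier trial in two- or three-vessel disease.
- **That every protocol-compliant PCI patient is angiographically incomplete.** Only those with a deferred or untreated lesion are, and CABG is not always complete either, given the vessel-size and feasibility limits.

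**Conclusion.** The point holds for completeness without needing any figure. It is determined after randomization by different rules in the two arms, so a PCI-versus-CABG contrast within its strata is not a randomized comparison. The direction and size of any bias cannot be derived from the documents. The 0.59 to 1.54 range shows only that a null effect can look substantial in either direction under the assumed completeness rates and risk gradients.

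For the Functional SYNTAX score the point is conditional. Low precision follows from the plan's own one-quarter expectation, taking 750 per arm and a 10-12% event rate. Bias arises only if measurement was selective or if unmeasured CABG patients are scored by angiogram; it is absent if the measured quarter is random and the others are excluded. The gap is the missing rule.

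The consequence is confined to the reading of exploratory subgroup tables. It is still worth correcting, because the list is pre-specified and the correction is small.

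**What to change.** Amend the subgroup section as follows:

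1. Limit between-arm (treatment-by-subgroup) analyses to variables fixed before randomization and measured in both arms. The core-lab angiographic SYNTAX score qualifies and should stay.
2. Report revascularization status only within each arm, labelled descriptive and non-randomized.
3. Restrict Functional SYNTAX score analyses to the PCI arm, or to within-arm analyses of patients with measured FFR.

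Do not bring in a new definition of complete PCI based on treating every lesion with FFR of 0.80 or below. Section 6 does not oblige the operator to stent at that level, so such a definition would again label some protocol-compliant patients incomplete.

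The cost is a few words in the list and no new data. Two exploratory between-arm tables are lost.
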